#### 5.3 Inclusion Criteria

- 1. Women aged 18-60
- 2. Singleton pregnancies
- 3. Patients undergoing elective LSCS via Pfannenstiel incision
- 4. Use of regional anaesthesia (epidural, spinal anaesthesia, or combined spinal-epidural)

#### 5.4 Exclusion Criteria

- 1. Multiple pregnancy
- 2. Patient undergoing non-elective CS
- 3. Caesarean section through midline laparotomy incision
- 4. Patients undergoing CS under general anaesthsia
- 5. History of chronic pain
- 6. Post-operative complications (haematoma, abscess, dehiscence, re-operation)

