## **PROTOCOL SYNOPSIS**

TITLE	Evaluation of the impact of fascial closure technique on post- operative pain in patients undergoing Pfannenstiel incision for Caesarean Section: A Randomised Trial
SPONSOR	DAN Women and Babies Unit, Sunnybrook Health Sciences Centre
FUNDING	DAN Women and Babies Unit, Sunnybrook Health Sciences Centre
ORGANISATION	
NUMBER OF SITES	1
RATIONALE	Caesarean sections are the most commonly performed surgical procedure throughout the world. Within the Canadian population, approximately one-third of all deliveries occur via Caesarean section. Chronic pain post-operatively has been identified as an issue that a large proportion of patients suffer with. As a result, a variety of surgical techniques have been undertaken, with some being compared to ascertain the reason for this chronic pain. One method which has been observed is related to the fascial layer and associated pain related to this layer. Whilst the abdominal fascia plays an integral role in ensuring the abdominal contents remain in situ. A variety of methods have been employed and studied to ensure the integrity of the fascial layer to reduce the risk of dehiscence, but no studies undertaken to date have evaluated the method of fascial closure and their effect on post-operative pain.
STUDY DESIGN	Randomised, double-blind, three-arm trial
PRIMARY OBJECTIVES	1. Analgesia use
	2. Pain score between three groups
NUMBER OF SUBJECTS	350
SUBJECT SELECTION	Inclusion Criteria:
	- Women aged 18-60 years
	- Women with singleton pregnancy
	
 
Patient undergoing elective lower segment Caesarean section via a Pfannenstiel Incision
 

	- Use of Regional Anaesthesia (epidural or spinal anaesthesia)
	Exclusion Criteria:
	- Multiple pregnancy
	
 
Patient undergoing non-elective Caesarean section
 

	- Caesarean section through midline laparotomy incision
	
 
Patients undergoing Caesarean section under General Anaesthesia
 

	- History of chronic pain
	
 
History of chronic pain
 
History of post-operative complications (haematoma, abscess,
 

	- History of post-operative complications (naematoma, abscess, dehiscence, re-operation)

	· · · · · · · · · · · · · · · · · · ·									
ARMS AND	Participants will be blinded to which method of fascial closure will									
INTERVENTIONS	be undertaken at the time of their surgery.									
	1. Single suture, knot above rectus fascia									

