#### 3.2 Secondary Objectives

Our secondary objective relates specifically to whether there is a difference in pain in patients undergoing primary or repeat caesarean sections. This will also be determined using sub-group analysis of participant pain scores based upon their questionnaire responses.

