## 5 SUBJECT SELECTION

#### 5.1 Study Population

Our study population includes all women undergoing elective primary or repeat lower segment Caesarean sections via a Pfannenstiel incision at Sunnybrook Health Sciences Centre in Toronto, Canada. This is a tertiary care centre with approximately 4000 deliveries annually and a Caesarean section rate of 18%. The average rate of Caesarean sections in most developed countries is approximately one-third of all deliveries.

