#### **10.2 Statistical Analysis**

For our primary outcome measure, we aim to perform statistical analysis using IBM® SPSS® Version. 26 Statistics Software for Windows to perform a two-sided T-test whereby comparing groups directly. Based upon an 80% power at an alpha of 0.05, we anticipate a 15% when comparing group 1 vs 2 and group 1 vs 3, we require a sample size of 255 participants across all three groups.

Specific to our subgroup analysis evaluating primary vs. repeat caesarean section, based upon an 80% power at an alpha of 0.05, we anticipate a 15% difference in comparing these two groups using a two-sided T-test. As a result, we require a sample size of 140 participants across these two groups.

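### The chronic-pain exclusion can remove repeat-Caesarean women because of how their earlier Caesarean turned out, so the primary-versus-repeat comparison is likely to be shifted, by an unknown amount, towards less pain in the repeat group

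*Combined protocol and SAP*

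**What the plan says.** Section 3.2 gives one secondary objective: "whether there is a difference in pain in patients undergoing primary or repeat caesarean sections". It has its own sample size. Section 5.2 asks for 140 women, 70 per group, at 80% power and a two-sided alpha of 0.05. Section 10.2 states the assumption behind it: "we anticipate a 15% difference in comparing these two groups using a two-sided T-test". No covariate adjustment is specified.

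Section 5.1 describes the study population as "all women undergoing elective primary or repeat lower segment Caesarean sections", without restriction by earlier outcome.

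The eligibility criteria do restrict it. Section 5.4 item 5 and the synopsis both exclude "History of chronic pain". Neither gives a cause, a look-back period or an exemption for pain that followed an earlier Caesarean. The complications criterion differs between the two places. The synopsis excludes "History of post-operative complications", while section 5.4 item 6 reads "Post-operative complications (haematoma, abscess, dehiscence, re-operation", with no mention of history.

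The synopsis rationale also states: "Chronic pain post-operatively has been identified as an issue that a large proportion of patients suffer with". It gives no rate.

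**The concern.** Every woman in the repeat group has had a Caesarean before, and no woman in the primary group has. If the earlier operation left a woman with chronic pain, item 5 removes her. The repeat group then loses some of the women with the worst previous experience of the outcome under study. The primary group cannot be filtered in that way, because its members have not yet had the operation.

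Randomisation gives no protection, since it balances the three closure arms and not primary against repeat status. The planned analysis contains nothing that addresses the selection, and the limitations in section 4.2 do not mention it. If repeat sections are truly more painful, part of the difference may be hidden. If there is no difference, repeat sections may look slightly less painful. Section 5.1 invites the reader to apply the answer to all repeat Caesareans, including the women who were screened out.

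**Working it through.** **1. Routes to exclusion, side by side**

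| Reason | Primary | Repeat |
|---|---|---|
| Chronic pain of other origin (both texts) | can exclude | can exclude |
| Chronic pain after an earlier Caesarean (both texts) | not possible | can exclude |
| Complication of other earlier surgery (synopsis wording) | can exclude | can exclude |
| Complication of an earlier Caesarean (synopsis wording) | not possible | can exclude |
| Complication of the index operation (a possible reading of section 5.4) | can exclude | can exclude |

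The second row is one-sided on any reading of the protocol. The fourth is one-sided only on the synopsis wording. The last applies to both groups, but after allocation, because section 7.3 randomises on the day of surgery.

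**2. The plan's own figure**

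Inputs from sections 5.2 and 10.2: 70 per group, two-sided alpha 0.05, power 80%. No SD or reference mean is given, so 140 can be neither confirmed nor refuted. Solving backwards for the standardised difference:

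- normal approximation: d = (1.960 + 0.842) × √(2/70) = 0.474
- t-test: d = 0.477

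**3. Illustrative size of the shift**

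The documents give neither the share of women excluded nor how much more pain they would have had. Both are assumptions here. Let p be the share of repeat women excluded, p0 the share of primary women excluded, and e the excess mean pain of excluded women over the rest, in SD, taken as equal in both groups. The net downward shift of the repeat mean relative to the primary mean is

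shift = (p − p0) × e.

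With p = 5% to 20% and e = 0.5 to 1.0 SD:

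- p0 = 0: from 0.05 × 0.5 = 0.025 to 0.20 × 1.0 = 0.20 SD
- p0 = 5%: from 0 to (0.20 − 0.05) × 1.0 = 0.15 SD
- p0 = 10%: from (0.05 − 0.10) × 1.0 = −0.05 to (0.20 − 0.10) × 1.0 = 0.10 SD

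The largest value is 0.20/0.477 = 42% of the detectable difference. A negative value arises only where primary women are assumed to lose the larger share.

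**4. Check with a second model**

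Suppose the worst share q of repeat women on the earlier outcome is removed, and that outcome correlates r with current pain. Then

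shift = r × φ(c)/(1 − q), with c = z(1 − q).

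- q = 5%, r = 0.2: 0.02 SD
- q = 20%, r = 0.5: 0.18 SD
- q = 10% to 20%, with 5% of primary women also removed and r = 0.2 to 0.5: net 0.02 to 0.12 SD
- equal shares removed from both groups, or r = 0: zero

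The two models agree on a range of about 0 to 0.2 SD when repeat women lose at least as large a share as primary women.

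**The case against.** The strongest reply is that excluding prior chronic pain is ordinary in a pain trial, that it applies to both groups, and that among women without such a history it restricts the population rather than biasing the comparison. Section 3.2 frames the question as a sub-group analysis of participants' scores, which can be read as concerning enrolled women only. This stands in part. It is why the size may be near zero and why the remedy is mainly one of wording. It does not remove the one-sided route, and section 5.1 sets no matching limit on the conclusion.

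Four stronger readings are tempting, and the documents do not support them:

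- **A bias of known size.** The share excluded and the excess pain are wholly assumed. The rationale's remark that chronic post-operative pain is common gives no rate and does not describe women presenting for elective repeat section.
- **A definite loss of power.** This would combine an assumed shift with 70 per group, which section 5.2 treats as a minimum. The plan needs 255 women and recruits 350, each of them primary or repeat, and the split is not stated.
- **The complications criterion certainly acts the same way.** That rests on the synopsis alone. Section 5.4 can be read as referring to the index operation.
- **The closure-arm comparison is untouched because the exclusions come before allocation.** This is true of chronic pain history. It is not established for item 6. If item 6 means complications of the index operation, it acts after randomisation and could affect the primary comparison.

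**Conclusion.** The concern holds in a limited form. Pain after an earlier Caesarean can exclude only repeat women, and the comparison is neither randomised nor adjusted. A conclusion about all primary and all repeat Caesareans is therefore likely to be shifted towards less pain in the repeat group. The direction assumes that women with chronic pain after an earlier Caesarean would report more pain after the next, and that repeat women lose the larger share to exclusion. The size is unknown. The figure of about 0 to 0.2 SD, against 0.477 SD detectable with 70 per group, is an illustration and not an estimate.

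For women who meet the criteria, the exclusion narrows the population and is not itself a bias. The complications part stays conditional until the synopsis and section 5.4 agree.

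**What to change.** 1. In sections 3.2 and 10.2, limit the conclusion to women who meet the eligibility criteria: no history of chronic pain and, if the reconciled text says so, no earlier post-operative complications. Report the result as a non-randomised association.
2. In section 10.2, and in the SAP that section 10 promises, replace the unadjusted t-test for this comparison with a linear model of pain score on primary or repeat status, adjusting for closure arm, age and body mass index. Arm is known from randomisation, and section 7.3 already collects the other two. State that this reduces other confounding but cannot restore the excluded women.
3. Reconcile the complications criterion in the synopsis with section 5.4 item 6, making clear whether it refers to earlier surgery or to the index operation.
4. Optionally, record how many women are excluded for chronic pain, by primary or repeat status, so that readers can judge the selection.

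The eligibility rule for chronic pain need not change. The cost is a narrower secondary claim, some redrafting and slightly more analysis work.

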## 6 **PROPOSED INTERVENTION**

All participants will undergo a lower segment Caesarean section via a Pfannenstiel incision. All participants involved in this study will undergo some form of regional anaesthesia (epidural, spinal, or combined spinal and epidural anaesthesia). Participants requiring general anaesthesia will be excluded from this study. Subsequently, the procedure is carried out and the delivery of

the foetus is undertaken. The hysterotomy is closed and haemostasis is then ensured in the intraabdominal cavity. At our unit, the peritoneum is not re-approximated.

Our proposed intervention involves three separate methods of closure of the rectus fascia which will be directly compared. Please refer to **Appendix A** to view diagrams outlining each method of fascial closure:

- 1) The first method of fascial closure involves the use of one #1 Polysorb™ Polyglactin 910 braided absorbable suture (Covidien™). At one angle of the rectus fascia, both the anterior and posterior leafs are grasped using Bonney forceps and the suture is tied behind this angle. This suture is then used to re-approximate the fascia in a continuous fashion across the incision. Prior to completing the suturing of this layer, the contralateral side is grasped with a Kocher clamp to bring the fascia forward so that the suture can be tied to itself behind the contralateral incision.
- 2) Method two involves two separate #1 Polysorb™ braided absorbable sutures (Covidien™). Both leafs of the rectus fascia are grasped using the Bonney forceps and the suture is placed behind the angle of the incision above the rectus fascia. Subsequent to this, the rectus fascia is reapproximated in a continuous fashion until the suture reaches the contralateral rectus abdominus muscle. Subsequently, a second #1 Polysorb™ suture is tied behind the contralateral angle in the same fashion and the remainder of the rectus fascia is reapproximated in a continuous fashion until both sutures are met, whereupon they are tied together.
- 3) The final method again involves two separate #1 Polysorb™ absorbable sutures (Covidien™). Both leafs of the rectus fascia are grasped with the Bonney forceps and the suture is placed behind the angle of the incision ensuring that the entire knot of the suture is below the rectus fascia. Subsequent to this, the suture is run in a continuous fashion to reapproximate the fascia until reaching the contralateral rectus abdominus muscle. Subsequently, a second #1 Polysorb™ suture is tied behind the contralateral angle in the same fashion and the remainder of the rectus fascia is reapproximated in a continuous fashion until both sutures are met, whereupon they are tied together.

The remainder of the procedure is completed whereupon the subcutaneous layer is inspected for haemostasis which is achieved using the electrocautery and is reapproximated if >2cm thickness with an absorbable suture. Subsequent to this, the skin is reapproximated using a 3-0 Caprosyn® (polyglytone\*6211) suture (CovidienTM) in a subcuticular fashion.

As a means of enhancing analgesia, our centre utilises epidural morphine standard as part of their regional anaesthesia for Caesarean Sections, this utilises a single-dose of 0.15mg morphine for spinal regional anaesthesia or a single-dose of 3mg morphine for epidural regional anaesthesia. Upon completion of the procedure, the patient receives one dose of diclofenac 100mg perrectum and is initiated on oral analgesia as regional anaesthesia wears off. The patient receives a standard analgesia regimen including Tylenol 1g orally every 6 hours, Naproxen 500mg orally every 12 hours, and hydromorphone 1-2mg orally every 4 hours as required for breakthrough

pain. They are subsequently discharged home with a prescription of these three medications for a short course.

## 7 STUDY TREATMENTS

#### 7.1 Method of Assigning Subjects to Treatment Groups

Up to 350 eligible patients will be randomly assigned to one of the three intervention groups in a 1:1 ratio using an Excel-based computer-generated randomisation scheme.

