#### 5.2 Sample Size

Our sample size is based upon a power of 80% at an alpha of 0.05 based on a two-sided t-test comparing groups. Based on these findings, our total sample size in each arm is 85 participants. In total, as there are three arms, our total sample size requires 255 participants, whereby randomising 85 participants to each group. In addition, we aim to undertake a sub-group analysis comparing primary to repeat Caesarean section with a power of 80% at an alpha of 0.05. Once again, a two-sided t-test would be used and based on these findings, we would require a total sample size of 140 participants, whereby comparing 70 participants per group. Given these minimum requirements and we estimate a drop-out rate of approximately 35%, we aim to recruit a total of 350 participants to this study.

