#### 7.3 Data collection method

Participants will be randomised to one of the three groups and will be provided a participant identification number on the day of their surgical procedure after consenting to proceed with the study. Subsequent to this, a chart review will be used to gather demographic information on participants, including age, gravida and para status, number of previous Caesarean sections, medical and surgical history, medication list, body mass index, and any obstetrical complications during the pregnancy. Participant's e-mails will be collected and saved in a separate document to maintain confidentiality.

Subsequent to this, participants will be e-mailed a link at each given time parameter to fill in their questionnaires which is a modified MD Anderson Brief Pain Inventory as a secure Google Docs Form (post-operative day #1 and 2, and at 2, 6 and 10 weeks post-operatively). As the participant's only identification is their participant identification number, this maintains participant confidentiality.

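### The arm comparisons in 10.2 are unadjusted t-tests, although the protocol plans for a 15% pain difference between primary and repeat Caesarean and collects that status: a small, nearly free gain in precision is left unused.

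*Combined protocol and SAP*

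**What the plan says.** - **Arm comparison.** Section 10.2 gives the planning effect as "we anticipate a 15% when comparing group 1 vs 2 and group 1 vs 3" and tests it with a two-sided t-test. The synopsis applies the same test to both primary endpoints, analgesia use over 72 hours and pain scores over 10 weeks. Neither place names a covariate.
- **Sample size.** Section 5.2 works from a "power of 80% at an alpha of 0.05 based on a two-sided t-test comparing groups" and concludes that "our total sample size in each arm is 85 participants".
- **Primary versus repeat Caesarean.** This is the only secondary objective (3.2). Section 10.2 says "we anticipate a 15% difference in comparing these two groups using a two-sided T-test", and 5.2 adds that "we would require a total sample size of 140 participants, whereby comparing 70 participants per group". Status is used only in this separate comparison.
- **Availability of the variable.** The chart review in 7.3 gathers "age, gravida and para status, number of previous Caesarean sections", among other items, and 10.1 lists previous Caesareans again. In 7.3 the chart review is described after randomisation.
- **Allocation.** Section 7.1 says women are assigned "using an Excel-based computer-generated randomisation scheme", with no stratification factor.
- **Later SAP.** The opening of section 10 says a detailed SAP will be written before the final analysis and may modify the plan. Nothing in the present text adds an adjustment.

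**The concern.** The protocol's planning value for primary versus repeat status, 15%, is the same as its planning value for the closure technique. If pain does differ by that much between the two kinds of section, the difference sits in the error term of an unadjusted t-test and widens the confidence interval for each arm contrast. Previous Caesareans are a fixed fact that allocation cannot alter, so they are a legitimate covariate.

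What is at stake is precision. The plan's own figures leave little to spare: 350 recruited less 35% is about 227 completers, below the 255 required. A covariate that is already collected recovers a little of that without enrolling anyone.

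**Working it through.** **Inputs from the documents:** two-sided alpha 0.05, power 80%, 85 per arm, 70 per primary/repeat group, 15% for both comparisons, 350 recruited, 35% drop-out.

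**Assumed, because the documents do not give them:** the SD of pain (back-solved below) and the primary share p, taken as 20% to 50%. Results are symmetric in p and 1-p, so this also covers 50% to 80%.

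**1. The plan's own figures.** The totals check: 3 × 85 = 255 and 2 × 70 = 140. With no mean or SD, 85 and 70 cannot be derived. They can be turned into the standardised effect they imply, d = (1.960 + 0.842) × √(2/n):
- n = 85: d = 2.802 × 0.1534 = 0.430 (0.432 by noncentral t)
- n = 70: d = 2.802 × 0.1690 = 0.474 (0.477 by noncentral t)

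The same 15% therefore implies an SD of 0.15/0.430 = 35% of the mean in one calculation and 0.15/0.474 = 32% in the other. I carry both values of d for the status effect.

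**2. Share of pain variance explained by status.** R² = p(1-p)d², with d in units of the overall SD:

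| d for status | p = 0.2 | p = 0.5 |
|---|---|---|
| 0.430 | 0.16 × 0.1847 = 3.0% | 0.25 × 0.1847 = 4.6% |
| 0.474 | 0.16 × 0.2243 = 3.6% | 0.25 × 0.2243 = 5.6% |

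Reading d in within-group SD units gives R²/(1 + R²) instead, which is 2.9% to 5.3%. Using 0.477 gives at most 5.7%.

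**3. Power for an arm contrast.** Completers per arm: 350 × 0.65 / 3 = 75.8. Power = Φ(0.430 × √(75.8/2) / √(1-R²) - 1.96).
- Unadjusted: Φ(2.646 - 1.96) = 75.4%
- R² = 3.0%: Φ(2.686 - 1.96) = 76.6%
- R² = 5.6%: Φ(2.724 - 1.96) = 77.8%

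By noncentral t, with 0.477 SD for status, power goes from 75.3% to 76.8%-77.7%. At the full 85 per arm it goes from 80.0% to between 81.1% and 82.2%. Put another way, 85 × (1-R²) gives 81 to 83 women per arm for the same power.

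**4. Is chance imbalance an additional harm?** Under simple randomisation the difference in primary share between two arms has variance 2p(1-p)/n. It therefore adds variance 2p(1-p)d²/n to a contrast whose total variance is 2/n. The ratio is p(1-p)d², which is the R² of step 2. At p = 0.5 and d = 0.474: √(0.5/75.8) = 0.081; 0.081 × 0.474 = 0.0385 SD; 0.0385² / (2/75.8) = 5.6%. It is the same quantity, and it is already in the t-test's standard error.

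**5. Adjustment or stratification?** Simulation with 85 versus 85, an even split, 0.474 SD for status and 40,000 runs per scenario:

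| Randomisation | Analysis | Power | Type I error |
|---|---|---|---|
| Simple | t-test | 79.9% | 4.9% |
| Simple | adjusted | 81.4% | 4.9% |
| Stratified | t-test | 80.2% | 4.3% |
| Stratified | adjusted | 81.7% | 5.0% |

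Adjustment brings nearly all the gain. Stratification adds about 0.3 points to it and, with a plain t-test, makes the test conservative.

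**The case against.** The strongest reply is that the gain is too small to matter: 1 to 2.5 power points, on figures that are all back-solved or assumed. The 15% is a planning value, and section 3.2 asks whether there is a difference at all. The SAP still to be written could add a covariate. Most of this stands. It settles the priority, but it gives no reason to leave out a term that costs one degree of freedom. A possible later SAP is where the change could be made; no present text makes it.

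Three stronger readings are tempting, and the documents do not support them:
- **That imbalance in primary/repeat status could pass for a closure effect.** Under randomisation the unadjusted contrast is unbiased and its error rate holds. Step 4 shows that the imbalance is the precision loss itself and must not be counted again.
- **That status is recorded before surgery, so stratifying is free.** Section 7.3 places the chart review after randomisation and does not time it against the operation. The fact exists earlier, but stratifying would require capturing it before allocation.
- **That the protocol specifies a single unstratified list, or treats status as an established predictor of pain.** Section 7.1 is merely silent on stratification, and the 15% is an assumption.

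**Conclusion.** The point holds as a minor, nearly free improvement to 10.2. If the planned 15% is 0.43 to 0.48 SD and the primary share is 20% to 50%, status explains about 3% to 6% of pain variance, and power at about 76 completers per arm rises from about 75% to about 76.5%-78%. If the true primary/repeat difference is smaller, so is the gain. For 72-hour analgesia use the documents give no expected primary/repeat difference, so the gain there cannot be sized. The planned t-tests are valid and unbiased, and nothing here threatens the trial's conclusions.

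**What to change.** In 10.2, and in the matching synopsis entry, replace the unadjusted t-tests with a linear model that has arm and primary/repeat status (no previous Caesarean versus one or more) as terms. Fit it for each primary endpoint, pain score and 72-hour analgesia use, and report 1 vs 2 and 1 vs 3 from it. The same model gives the primary-versus-repeat contrast adjusted for arm. Fix this before the data are unblinded, either by amendment or in the promised SAP.

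The cost is one sentence and no new data.

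Stratifying in 7.1 is optional. It would need a separate list for each group, status captured before allocation, staff choosing the correct list, and all of this in place before enrolment. If it is adopted, the model must still include status. If enrolment has begun, make the analysis change alone.
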